Methods: This is a single arm study to assess the effectiveness of an experimental telehealth intervention within the treatment of ESLD, and compare it with a historic cohort. All inpatients with advanced liver disease and at least 1 complication will be eligible to participate. The study group receives the Telehealth intervention and will be given an ipad/smartphone preloaded with the instruments used for symptom monitoring and cognitive function assessment during the hospital admission. A research coordinator will consent the patients and conduct a 30-minute introduction to use of device on the day of enrollment (within 24-48 hours of admission). The second assessment will be done on day 2, and third assessment on day of discharge. After that, the patient will be told to do the study assessments daily at home. The study assessment results will be reviewed by the providers on the same day, and based on the severity scores clinical actions will be taken and documented.

IV. Expected Research Outcomes and Benefits -
--

Primary Outcomes:

- 1) Healthcare utilization (30 and 90-day readmission)
- 2) Changes in severity scores of symptoms and quality of life over time.

3) Patient experience/satisfaction.

Benefits of the research: Applying telehealth intervention (inclusive of remote monitoring of symptoms and cognitive function) with a well-defined clinical algorithm at the time of discharge of patients with ESLD, who are prone to impaired quality of life, adds a **new dimension** to the care delivery model. This new post-hospital discharge algorithm is expected to have positive effects on many parameters, including readmission rates, patient satisfaction, and above all on the health outcomes. Arguably, these improvements will reduce health care costs among a group of patients with ESLD, who are high utilizers of healthcare services. Benefits to individual patients include monitoring of their own symptoms, and cognitive function, which will allow early detection of hepatic encephalopathy and/or other complications.

VII. Evaluation Component and Research Evaluative Procedures - Oversight and Statistical Tests

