Oversight: The PI will be overseeing the implementation of the project along with the Co-Investigator. Since the study involves patients who are admitted to the hospital, and offers them a device to improve their own care, the likelihood of participation is high. We will assess the attrition rates and other technical issues during the project. Higher rates of no response to timed assessments from enrolled patients will trigger an alert to the research coordinator, who will then call the patients to make sure device is working appropriately and explore the reasons for missing responses. Furthermore, a detailed discussion at the time of enrollment about the project and expected responsibilities from patients will reduce the missing data points.

Statistical Tests: The data for study group will be described using both graphic and summary statistics. Process data on participation, usage and satisfaction with telehealth intervention will be collected and summarized to assess intervention fidelity. We will assess the change in percent readmissions at 30 days and 90 days in the study group from baseline to 3 months. The average rate of change in the defined outcomes in longitudinal (overtime) analyses using paired t tests and 95% CIs of the differences in the two groups will be conducted. The trajectories of symptom and quality of life scores will be illustrated by graphing individual patient values over time course of the study for the intervention group. We will test whether the relationship between study outcome and study arm differ with the severity of disease as assessed by MELD (Model for End Stage Liver Disease) score using two-way analysis of variance for repeated measures.

(B) Performance Measures

B) Performance measures:

- 1) Number of patients enrolled in the study.
- 2) Completion of 7, 28 days and 3 months assessment of symptoms and cognitive function by the patients.

- 3) Attrition rates of enrolled patients.
- 4) Efficiency of the technical device provided to patients as assessed from ease of use by patients and providers.
- 5) Scholarly activities (publications and presentations) resulting from study data.

VIII. Health Disparities

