“HGE healthcare solutions” is a group of experts who have pioneered some work in telehealth, and created a smartphone based COPD app (Chronic Obstructive Pulmonary Disease), which assesses daily symptoms and triggers alerts to providers for immediate treatments. This app has shown to improve health outcomes and reduce hospitalizations by changing the approach of health care to proactive than reactive. ^{v vi} We will be partnering with this company in creating and delivering our telehealth intervention. The company operates on a HIPAA secured platform, which maintains confidentiality and security of the data. They also offer technical assistance to end users during normal business hours.

(3) Research Design, Methods and Activities -
--

Methods: This is a single arm trial to assess the effectiveness of an experimental telehealth intervention within the treatment of ESLD, and compare it with a historic control. The study patients continue to receive the routine standard of care, which may involve addressing symptoms based on individual needs and circumstances. All participants will be given an ipad/smartphone preloaded with the instruments used for symptom monitoring and cognitive function assessment. A research coordinator will consent the patients and conduct a 30-minute introduction to use of device on the day of enrollment. Repeat assessments will be done as shown in **Table 1** above. All patients will receive the standard of care discharge planning, including discharge instructions and a confirmed follow-up ambulatory visit within 2-4 weeks.

Inclusion Criteria: All patients being discharged from the inpatient liver practice of the Einstein Healthcare Network (EHN) who meet the following criteria will be eligible.

- ✓ Patients must be age 18 years or older
- ✓ Ability to provide informed consent, and must be able to cognitively answer questionnaires
- ✓ Patients who received a diagnosis of Advanced Liver Disease with at least 1 of the complications (Hepatorenal Syndrome, Portal Hypertension, Ascites, Hepatic Encephalopathy)
- ✓ Patient must be able to read/ speak English
- ✓ Patient must have a support person

Exclusion Criteria:

- ✓ Cognitive impairment which precludes participation
- ✓ Projected survival, in the opinion of the provider, of less than six months
- ✓ Current psychosis or confusion, precluding a patient from being consented
- ✓ Patients being discharged to nursing homes

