- ✓ Patients with red green color blindness (as they will not be able to respond to stroop test questions).

Telehealth Intervention:

Patients will receive a 30-minute introduction to the use of ipad/smartphone, and instructions to respond to the following assessments. Initial assessments will be performed on the day of enrollment, and all of them will be repeated periodically (**Table 1**), for a total of 3 months study

participation. The assessments include the following: Pain (severity, location), shortness of breath (at rest or with mild activity), cognitive function assessment (drowsy, hard time concentrating, irritable, trouble remembering things, slurred speech, unsteady gait), and stroop test (color matching test, one cycle lasts 45 seconds).

Weight monitoring: Monitoring weight will allow assessment of fluid retention in ESLD patients, and help detect any development/ worsening of ascites. Patients will be instructed to enter their daily weights for the first month, and then every week for next 2 months. Any weight gain of more than 2 lbs within 1-2 days for 3 consecutive days will trigger a phone call by the providers.

A simplified step by step guide summarizing the instructions will be included with the device. Patients will be given a toll-free number that will be available during work hours (9am to 5pm) for any technical issues, and will be urged to complete assessments by 11 am on a daily basis.

Site: Levy 7 is the home of the “Liver Care Center at Einstein”, a 15 bed inpatient unit dedicated to the care of patients with liver disease. This inpatient unit is the site of identification and recruitment of patients in this project.

Recruitment methods: The research coordinator will contact eligible patients within 24-48 hours of admission and conduct informed consent. All patients who consent will be then randomized to either of the 2 groups. We assume 3-4 patients will be enrolled per week, for 7 months of enrollment period.

Sample size and power: Assuming a baseline risk of readmission in the historic control of 40% and 10% attrition rates, a sample size of 50 patients will be sufficient to detect a difference of 35% or greater in the intervention group. Accepting a type I error rate of no more than .05, and a Type II error rate of .20, we will have 80% statistical power to detect a difference of this magnitude or larger.

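### The stated 80% power for 50 patients does not fit the declared single-arm, historic-control design, whether the 35% difference is absolute or relative

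*Combined protocol and SAP*

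**What the plan says.** Section II (Methods) declares the design: "This is a single arm study to assess the effectiveness of an experimental telehealth intervention", compared with a historic cohort. Section XI (3), Methods, repeats it ("This is a single arm trial to assess the effectiveness of an experimental telehealth intervention") with a historic control.

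The only power calculation is in Section XI (3), Sample size and power. It takes a 40% readmission risk in the historic control, 10% attrition, type I error .05 and type II error .20, and concludes that "a sample size of 50 patients will be sufficient to detect a difference of 35% or greater in the intervention group" and that "we will have 80% statistical power to detect a difference of this magnitude or larger".

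Other text does not sit easily with a single arm of 50:

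- Section XI (3), Recruitment methods: "All patients who consent will be then randomized to either of the 2 groups".
- The same paragraph, on accrual: "We assume 3-4 patients will be enrolled per week, for 7 months of enrollment period".
- Section VII, Statistical Tests: "95% CIs of the differences in the two groups will be conducted", and "We will test whether the relationship between study outcome and study arm differ with the severity of disease". It does not say whether these mean randomised arms or study versus historic patients.

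**The concern.** The power statement leaves out what is needed to check it: whether 35% is absolute or relative, whether the test is one- or two-sided, which test is meant, whether 40% is the 30-day or the 90-day rate (Section IV lists both), and how many patients the historic rate comes from. Filling these gaps in the natural ways for a single-arm comparison does not give 80%.

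Readmission is the first-listed primary outcome, and this is its only sample-size justification. If 35% is absolute, the plan understates what 50 patients can detect. If it is relative, a true effect of that size would be missed about 38% of the time (one-sided) to 52% (two-sided) against a fixed 40%, not the stated 20%, and a null result could be over-read as showing no benefit. If the randomisation sentence were followed with the 50 split 1:1 (an assumption), power on the relative reading would fall to about 17% two-sided or 26% one-sided.

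**Working it through.** **Inputs from Section XI (3), Sample size and power.** Historic rate p0 = 0.40; 50 enrolled; 10% attrition, so 50 × 0.9 = 45 evaluable; α = .05; power 80%. The alternative is p1 = 0.40 − 0.35 = 0.05 if 35% is absolute, or p1 = 0.40 × (1 − 0.35) = 0.26 if relative. Sidedness is not given, so both are shown.

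**Step 1: where 50 comes out.** Two equal arms, pooled normal formula, two-sided .05, with p̄ = (0.40 + 0.05)/2 = 0.225:

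n per arm = [1.960·√(2·0.225·0.775) + 0.842·√(0.40·0.60 + 0.05·0.95)]² / 0.35² = 21.1, so 22.

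The total is 44, and 44/0.9 = 48.9, so 49, close to the stated 50. Power with 22 per arm is 81.7%. A one-sided calculation with continuity correction also gives 22 per arm and 49. On the relative reading the two-sided two-arm formula needs 176 per arm, so it does not explain 50.

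**Step 2: the declared single-arm design against a fixed 40%, 45 evaluable.** Normal approximation:

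power = Φ{ [(p0 − p1)√n − z·√(p0(1 − p0))] / √(p1(1 − p1)) }

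- p1 = 0.26, two-sided: (0.14 × 6.708 − 1.960 × 0.490)/0.439 = −0.05, power 48.1%.
- p1 = 0.26, one-sided (z = 1.645): 0.30, power 61.9%.
- p1 = 0.05, two-sided: (0.35 × 6.708 − 0.960)/0.218 = 6.4, power above 99.9%.

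The exact binomial test agrees. Two-sided, it rejects at 11 or fewer readmissions or at 26 or more (size 3.4%). One-sided, it rejects at 12 or fewer (size 4.5%).

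| Exact test, n = 45, fixed 40% | Two-sided | One-sided |
|---|---|---|
| Power, 40% to 5% | >99.9% | >99.9% |
| Power, 40% to 26% | 48.4% | 61.7% |
| Rate at which power is 80% | 20.6% (19.4 points, 49% relative) | 22.6% (17.4 points, 44% relative) |
| Evaluable needed for 80%, 40% to 5% | 12 | 10 |
| Evaluable needed for 80%, 40% to 26% | 92–98 | 74–79 |

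The ranges in the last row run from the first n that reaches 80% to the n from which power stays at or above it; exact power is not monotone in n.

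Counting all 50 patients does not help. At 26%, the normal approximation gives 52.7% two-sided and 66.3% one-sided; the exact test gives 44.6% and 57.4%, lower than at 45 only because the cut-off moves in whole patients.

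**Step 3: the 40% estimated from a finite cohort.** The documents give no cohort size; 45 and 200 are assumed. Pooled two-sample normal approximation, 45 study patients:

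| Assumed cohort | Power at 5%, two-sided | Power at 26%, two-/one-sided | 80%-power difference, two-/one-sided |
|---|---|---|---|
| 45 | 98.7% | 29% / 41% | 26 / 23 points |
| 200 | >99.9% | 41% / 55% | 21 / 19 points |

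**Step 4: the randomisation sentence taken literally.** With 22.5 evaluable per group (1:1 assumed), power for 40% versus 5% is 82.6% two-sided. For 40% versus 26% it is 16.5% two-sided or 25.7% one-sided.

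**Step 5: accrual.** Seven months is 7 × 52/12 = 30.3 weeks; 3 to 4 per week gives 91 to 121 patients, about twice 50.

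**The case against.** The strongest reply is that the text speaks of a difference, not a relative reduction, and that the reconstruction in Step 1 works only on the absolute reading. On that reading 50 is indeed sufficient, power is higher than claimed, and no patient or conclusion is harmed. That stands as far as it goes: the evidence leans towards the absolute reading, and on it the study is not underpowered. But the 80% is still wrong for the declared design, the document never says which reading applies, and a reader could take 35% as a relative reduction.

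A second point is that the headline percentages treat 40% as fixed, while Section II speaks of a cohort. That is fair, and Step 3 shows the effect. A finite cohort does not rescue the relative reading at any size, because a fixed 40% is its ceiling. On the absolute reading, power falls to about 80% two-sided only with roughly 10 historic patients (79.9% by the pooled approximation), and nothing in the documents suggests so small a cohort.

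Third, the accrual figure is an assumed rate rather than a target and has no bearing on the power arithmetic. That is correct. It is listed only because it too is inconsistent with a total of 50 and should be reconciled in the same edit.

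**Conclusion.** The concern holds. Against a fixed 40% with 45 evaluable patients, the stated 80% is too low if 35% is absolute (above 99.9%) and too high if it is relative (48% two-sided, 62% one-sided). The conclusion is the same for one- or two-sided tests, exact or normal methods, 45 or 50 patients, and the assumed cohorts of 45 and 200. What 45 patients can detect with 80% power lies between the two readings: 17 to 19 points against a fixed 40%, or 19 to 26 points against those cohorts. The match to a 1:1 two-arm total suggests a carry-over from a two-group plan, but that is inference; the mismatch does not depend on it. It must be corrected because it is the only sample-size justification for the first-listed primary outcome.

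**What to change.** In Section XI (3), Sample size and power, restate the calculation for the single-arm comparison with 50 enrolled and 45 evaluable. State:

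- whether the difference is absolute or relative;
- the test and its sidedness;
- the 30- or 90-day window to which the 40% belongs;
- whether 40% is a fixed benchmark or an estimate, and if an estimate, the cohort and its size.

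As an illustration for a fixed benchmark: with 45 evaluable patients, an exact two-sided .05 test against 40% has 80% power for a fall to about 20.5%, that is 19 to 20 points or 49% relative. Against an assumed cohort of 45 or 200, the two-sided figure is about 26 or 21 points. If a 35% relative reduction was intended, give the lower power that 50 patients provide.

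Reconcile with the single-arm design the randomisation sentence and accrual figure in Recruitment methods, and the two-group and study-arm wording in Section VII.

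Cost: wording only if 50 is kept, though on the relative reading the stated power becomes less favourable. If the sponsor wants 80% power for a 35% relative reduction against a fixed 40%, enrolment rises to about 103–109 two-sided (92/0.9 to 98/0.9) or 83–88 one-sided (74/0.9 to 79/0.9), and further against a finite cohort.

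### Only the 50 treated patients are sized and the historic cohort's number is never fixed, so the stated 80% power and the precision of the readmission comparison do not belong to this design

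*Combined protocol and SAP*

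**What the plan says.** Section II (Methods) describes a single-arm study that will "compare it with a historic cohort". Section XI (3) repeats this with a historic control and says that all participants receive the device.

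Section XI (3), Sample size and power, starts from "Assuming a baseline risk of readmission in the historic control of 40% and 10% attrition rates" and states that "a sample size of 50 patients will be sufficient to detect a difference of 35% or greater in the intervention group". The error rates are given as "Accepting a type I error rate of no more than .05, and a Type II error rate of .20", followed by the claim that "we will have 80% statistical power to detect a difference of this magnitude or larger". It does not say whether the test is one- or two-sided, which test it is, whether 35% is absolute or relative, or whether 40% refers to 30 or 90 days.

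Two other places bear on the comparison. Recruitment methods, in the same section, still says that "All patients who consent will be then randomized to either of the 2 groups". Section VII (Statistical Tests) plans that "95% CIs of the differences in the two groups will be conducted", although its sentence on readmission speaks only of change within the study group and does not mention the historic cohort.

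No section gives the historic cohort's size, period or source.

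**The concern.** Readmission is the first primary outcome listed, and its comparator is a sample of past patients. Two sample sizes determine the power and interval width of such a comparison, and the plan gives one. Until the second is fixed, a power of 80% cannot be attached to the design, and a reader cannot tell how precise the readmission estimate will be.

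The gap also leaves the analysis open. The 40% could be carried into the analysis as a known constant, so that chance error in the historic rate passes into the conclusion. The cohort could also be chosen, or its size settled, after the study results are known. A small cohort would widen the interval when record review could narrow it without enrolling anyone.

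**Working it through.** **Inputs.** From Sample size and power: control rate p0 = 0.40; 50 enrolled and 10% attrition, so 50 x 0.9 = 45 evaluable; alpha .05, taken as two-sided; target power 80%. The 35% is read both ways: absolute, 40% to 5%; relative, 40% x 0.65 = 26%. The historic size m is not in the documents, so 45, 100 and 200 are assumptions chosen to show the range.

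**Step 1: reproduce the 50.** Two-sample formula, equal arms, p̄ the mean of the two rates:

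n per arm = [1.96 √(2p̄(1−p̄)) + 0.842 √(p0(1−p0) + p1(1−p1))]² / (p0 − p1)²

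For 40% v 5%, p̄ = 0.225: (1.157 + 0.451)² / 0.35² = 21.1, so 22 per arm. With attrition, 22/0.9 = 24.4, so 25 per arm and 50 in total. This matches the plan. A one-sided calculation with continuity correction also gives 22 per arm.

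Other readings do not give 50:

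| Calculation | After attrition |
|---|---|
| One sample v fixed 40%, absolute 35 points | about 9-12 |
| One sample v fixed 40%, relative 35% | about 78-100 |
| Two-sample, relative 35% | about 309-392 in total without continuity correction |

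**Step 2: power of the design described, 45 v m.** With p̄ now the weighted mean rate:

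power = Φ{[(p0 − p1) − 1.96 SE0] / SE1}, where SE0 = √(p̄(1−p̄)(1/45 + 1/m)) and SE1 = √(p1(1−p1)/45 + p0(1−p0)/m)

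Example, 40% v 26%, m = 45: p̄ = 0.33, SE0 = 0.0991, SE1 = 0.0980; (0.14 − 0.1943)/0.0980 = −0.55; power 29%.

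**Step 3: precision.** 95% half-width = 1.96 √(0.4 x 0.6/m + 0.26 x 0.74/45). For m = 45: 1.96 √(0.00533 + 0.00428) = 0.192. For m = 200: 1.96 √(0.00120 + 0.00428) = 0.145.

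| m | Power, 40% v 5% | Power, 40% v 26% | Half-width, 40% v 26% | Smallest difference with 80% power |
|---|---|---|---|---|
| 45 | 98.7% | 29% | 19.2 points | about 26 points |
| 100 | 99.9% | 36% | 16.0 points | about 23 points |
| 200 | above 99.9% | 41% | 14.5 points | about 21 points |
| no limit | above 99.9% | about 48% | 12.8 points | about 19 points |

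**Step 4: the conditional case.** Suppose 40% were estimated from m patients and then used as a constant in a one-sample z test. The test would use variance p(1−p)/45, but the true variance is larger by the factor 1 + 45/m. Hence

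two-sided type I error = 2[1 − Φ(1.96/√(1 + 45/m))]

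For m = 45: 1.96/√2 = 1.386, giving 16.6%.

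| Test against 40% as a constant | m = 45 | m = 100 | m = 200 |
|---|---|---|---|
| Two-sided z test | 16.6% | 10.4% | 7.7% |
| One-sided 5% z test | 12.2% | 8.6% | 6.9% |
| Two-sided exact binomial test | 14.5% | 8.0% | 5.7% |
| False claims of benefit only (lower tail of the two-sided z test) | 8.3% | 5.2% | 3.8% |

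**The case against.** A reader might infer that the plan treats 40% as known exactly and that its real type I error is therefore about 10-17%. The documents do not support this. An assumed control rate is an ordinary input to any two-group calculation, no section names a one-sample test against 40%, and Section VII names intervals for a difference between two groups. The arithmetic also points the other way: among the variants tried, only two-sample calculations reproduce 50, and these already allow for sampling error in a control group of 22-25. The inflation figures need a test that the plan does not specify and a cohort size that it does not give.

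It can also be said that cohort size hardly matters to the power claim. If 35% is absolute, 45 patients reach about 82% power with only 11 historic patients. If it is relative, no cohort size takes power above about 48%. This stands: fixing m does not by itself decide whether 80% is met. It does not make the 80% figure right for this design, and the interval depends on m under both readings.

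Finally, a target of about four charts per study patient is a rule of thumb, and a 15-bed unit may not have that many comparable patients. Support person, projected survival and willingness to consent may not be recoverable from records. These limits are real and are carried into the fix.

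**Conclusion.** The concern holds as a mismatch between the sample-size statement and the design. The 50 is consistent with a randomised 25 + 25 comparison, like the leftover sentence on two groups. That is an inference from the arithmetic and does not prove how the number was reached. For 45 evaluable patients against a historic cohort, the stated 80% describes neither reading of 35%: power is about 99% or more if absolute (with at least 45 historic patients), and 29-48% if relative.

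Precision is likewise undefined. For 40% v 26% the half-width runs from 19.2 points with 45 historic patients to 14.5 with 200, against a floor of 12.8 set by the 45 study patients.

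The type I error of about 17%, 10% or 8% is conditional on a two-sided z test against 40% as a constant, and is lower with an exact test. It is a reason to exclude that analysis, not a finding about the analysis planned.

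All figures rest on 45 evaluable patients, a two-sided .05 level unless marked otherwise, normal approximations except for the exact test, and assumed cohort sizes. The point should be settled before enrolment.

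**What to change.** - Define the comparator before enrolment: all patients discharged in a fixed historic period who meet the criteria that can be checked in charts, one index discharge each. Aim for about 180-200 if available, and report how many the rule yields.
- Estimate the readmission difference, at 30 and at 90 days, with a two-sample interval that carries the sampling error of both groups. State that the study rate will not be tested against 40% as a constant.
- Restate the power sentence for 45 study patients v that number. Give the sidedness, the readmission window to which 40% refers, and whether 35% is absolute or relative. If it is relative, say plainly that power stays below about 48%.
- Reconcile the randomisation sentence with the single-arm design.

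**Cost.** More chart extraction, with no new patients, and possibly a less favourable power statement. The gain is limited: going from 45 to 200 charts narrows the half-width by 19.2 − 14.5 = 4.7 points, and going from 100 to 200 by 16.0 − 14.5 = 1.5 points. The availability of comparable charts is an assumption; the plan mentions medical records only for enrolled patients' clinical data. A larger cohort does not remove bias from case mix, calendar period or selection, so the report should not present a narrower interval as protection against it.
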